6.7. Safety

For all Safety Tables, data in Part A and Part B will be summarized as follows, unless otherwise specified:

- Part A summarized with all subjects for the entire time (Week 0 to Week 32)
- Part B, for Period 1, will include the first 16 weeks until the first dose of treatment administered in Period 2 at or after Week 16, summarized by the randomized treatment arms and the combined placebo group (Placebo QW/ Placebo Q2W; Izokibep QW; Izokibep Q2W), and includes all subjects who received at least one dose of study treatment. AEs will be included if date of onset is on or after the day of the first dose received in Period 1 and before the date of the first dose received in Period 2. If a subject did not receive any dose of study treatment in Period 2, all AEs with onset on or after the day of first dose received in Period 1 through 4 weeks (28 days) after the last dose received will be included.
- Part B, Period 2, will include data collected on and after the first dose of study treatment administered at Week 16 visit (or after Week 16 visit, if Week 16 visit is missing), summarized by the randomized treatment groups (Placebo Izokibep QW; Placebo Izokibep Q2W; Izokibep QW; Izokibep Q2W), and includes all subjects who took at least one dose of study treatment in Period 2. AEs will be included if date of onset is on or after the day of first dose received in Period 2 through 4 weeks (28 days) after the last dose received.

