- ^c Vital signs include measurements of temperature, respiratory rate, systolic and diastolic blood pressure, and pulse. Measurements should be taken in a sitting position after 5 minutes of rest.
- d Electrocardiograms in triplicate will be recorded after subject has been supine for at least 5 minutes.
- ^e Chest x-ray (posterior/anterior or anterior/posterior) will be performed at screening for subjects who do not have a chest x-ray available within 3 months of screening. Women of childbearing potential must have negative pregnancy test before x-ray is performed.
- f Serious adverse events will be recorded from the signing of informed consent through the 8-week follow-up visit (ie, 8 weeks after the last dose of study drug); adverse events will be recorded from Day 1 (ie, administration of study drug) until 4 weeks after the last dose of study drug.
- ^g Confirm ongoing antiseptic wash requirement at every visit. From Screening through Week 16, subjects will complete a daily diary of their analgesic use. From Week 16 through Week 32, subjects will be required to tell site staff if they took any analgesics within 24 hours of their site visit. See Section 10.10. Subjects will refrain from taking analgesics 12 hours before the site visit, if possible.
- ^h Lesion count will be performed at every study visit marked in the Schedule of Activities and must address all relevant anatomical regions in each subject. The AN count includes counts of draining tunnels (fistulas and sinuses). See Section 8.1.1 for more details. Any unscheduled visit for disease worsening based on the investigator judgment will include AN count and will be recorded in the appropriate CRF.
- ¹From screening through Week 16, subjects will complete a daily diary of their skin pain. See Section 8.1.5. No in-site assessment of skin pain will be completed at the Week 16 visit. From Week 16 through Week 32, subjects will complete skin pain assessments at the site. Note: subjects may not be randomized if pain diaries are not completed for ≥ 3 out of 7 days (at a minimum) prior to the Day 1 visit.
- ^j For subjects who consent to the optional photography substudy at selected sites, photographs will be taken.
- ^k QuantiFERON® test or PPD test for TB will be performed. Note: T-SPOT® testing may be allowed after consultation with medical monitor.
- ¹Serum pregnancy test required for screening and urine pregnancy test required at all other times for women of childbearing potential.

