- ^m Pharmacokinetic and ADA blood sampling will be taken prior to administration of study drug (pre-dose) on dosing days.
- ⁿ Administration of study drug should be done last after all study procedures unless indicated otherwise. Subjects will be monitored at the study site for at least one hour after study drug administrations at the following visits: for subjects enrolled to QW arms, on Day 1 and Weeks 1, 16, and 17; for subjects enrolled to Q2W arms, on Day 1 and Weeks 2, 16, and 18. After Week 4, qualified subjects may perform home dosing of study drug at weeks without study visits (see footnote a) and do not need to return to the clinical site on those weeks. Subjects may begin self-administration of study drug from Week 5 (QW dosing) or Week 6 (Q2W dosing). Subjects will be trained on study drug handling and self-administration of study drug at the study visits prior to beginning self-administration. A subject's caregiver or designee can also be trained on home dosing based on the subject's preference. Study-site staff will administer study drug at the first 2 visits. Thereafter, if home dosing is a consideration, the subject or subject's caregiver or designee must administer and demonstrate competency

for at least 2 visits prior to being allowed to dose at home. Otherwise, the subject will need to return to the site for all injections. The last dose of study drug for subjects dosed QW is Week 31 and for subjects dosed Q2W is Week 30.

[°] A dosing diary will be completed for every home dosing administration.

^p Subjects who end the study early will complete an early termination visit and complete the procedures described at the Week 32 visit within 2 weeks of the last dose of study drug.

2. Introduction

Izokibep is a potent and selective inhibitor of interleukin 17A (IL-17A) that is being developed for treatment of hidradenitis suppurativa (HS).

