8.3.1. Time Period and Frequency for Collecting AE and SAE Information

All SAEs will be collected from the signing of the ICF until the 8-week follow-up visit as specified in the SoA (Section 1.3).

All AEs will be collected from the first dose of study drug until 4 weeks after the last dose of study drug as specified in the SoA (Section 1.3).

Medical occurrences that begin before the start of study drug but after obtaining informed consent will be recorded as medical history/current medical conditions, not as AEs.

All SAEs will be recorded and reported to the sponsor or designee immediately and under no circumstance should this exceed 24 hours from investigator's knowledge of the event, as indicated in Section 10.3.4. The investigator will submit any updated SAE data to the sponsor within 24 hours of it being available.

Investigators are not obligated to actively seek information on AEs or SAEs after the conclusion of the study participation. However, if the investigator learns of any SAE, including death, at any time after a subject has been discharged from the study, and he/she considers the event to be reasonably related to the study drug or study participation, the investigator must promptly notify the sponsor/designee (see Section 10.3.4).

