5.1.3. Treatment Period

Data collected on Day 1 will be assigned to the Treatment Period unless the time (HH:MM) of data collection and time (HH:MM) of the first dose of study drug are both recorded and the data collection time is before the time of the first dose of study drug. In this case, the assessment will be assigned to the screening period. If the time (HH:MM) of data collection is not recorded but the protocol and/or CRF includes an instruction to the effect that all Day 1 assessments are to be performed prior to the first dose of study drug, the data collected at Day 1 will be assigned to the screening period. However, adverse events and concomitant medications starting on Day 1, will be assigned to the Treatment Period, unless the time (HH:MM) demonstrates otherwise.

The Treatment Period is defined as the period from the date/time of the first dose of study drug to Week 32 (four weeks after the last dose) or early termination/end of treatment visit (within two weeks from the last dose).

Treatment will be divided into two periods, Period 1 and Period 2. In Part B, Period 1 will start at the first dose of study drug and end at Week 16 when Week 16 assessments are completed and before administration of study drug. Period 2 will start at the time of first administration of study drug at or after Week 16 and end at Week 32 or early termination/end of treatment visit.

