6.7.2. Adverse Events

All SAEs will be collected from the signing of the ICF until the 8-week follow-up visit. All AEs will be collected from the first dose of study drug until 4 weeks after the last dose of study drug. All AEs recorded on the CRF will be coded using the latest MedDRA dictionary around the time of Database Lock and classified as either AEs or TEAEs as follows:

- TEAEs for Part A and Period 1 in Part B are either events with start date and time after the start of the Treatment Period and up to 4 weeks after the end of the Treatment Period (for subjects in Part A or those who don't enter Part B Period 2), or events with start date and time prior to the start of the Period 1 whose severity worsens on or after the start of Period 1 and up to 4 weeks after the end of the Treatment Period (for subjects in Part A or those who don't enter Part B Period 2).
- TEAEs for period 2 in Part B are either events with start date and time after the start of administration of Week 16 treatment and up to 4 weeks after the end of the Treatment Period, or events with start date and time prior to the start of administration of Week 16 treatment whose severity worsens on or after the start of administration of Week 16 treatment through 4 weeks after the end of the treatment period. For subjects who receive treatment in period 2, TEAEs with start date after the start of period 2 will be assigned to period 2 only, not to period 1.
- Treatment-Emergent Serious AEs (TESAEs) will be defined as TEAEs which meet the criteria as Serious = "Yes".
- The relationship between a TEAE and treatment is assessed as related or not related. A treatment-related TEAE will be defined as a TEAE considered by the investigator as related to treatment or with unknown/missing relationship to treatment.
- Assessment of AE intensity will be based on CRF AEs form. Severe TEAEs are defined as TEAEs assessed as being "Severe" in intensity and include those events where the intensity is missing.
- TEAEs leading to discontinuation of treatment are defined as TEAEs where "Action Taken with Study Treatment" is indicated as "Drug Withdrawn".
- Injection site reactions (ISRs) will be defined as any adverse event where the preferred term contains the words "injection site".

In addition to the aforementioned AE types, the following TEAEs of special interest will be summarized:

- Candida infection,
- Inflammatory bowel disease,
- Suicidal ideation.
- Malignancies

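### The adverse-event cut-offs in SAP 6.7 and 6.7.2 conflict, rest on a misdated Week 32, and leave part of the 8-week SAE window out of the tables

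*SAP*

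**What the plan says.** Three boundaries apply to the same family of adverse-event tables.

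- **SAP 6.7, Part B.** Events count "through 4 weeks (28 days) after the last dose received". This covers Period 2, and Period 1 for anyone with no Period 2 dose.
- **SAP 6.7, Part A.** The summary span is Week 0 to Week 32.
- **SAP 6.7.2, both parts.** Treatment emergence extends "up to 4 weeks after the end of the Treatment Period". SAP 5.1.3 takes that period "to Week 32 (four weeks after the last dose) or early termination/end of treatment visit", the latter being "within two weeks from the last dose".

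The dosing schedule is in the footnotes to Protocol 1.3: "The last dose of study drug for subjects dosed QW is Week 31 and for subjects dosed Q2W is Week 30".

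On collection, Protocol 8.3.1 states: "All SAEs will be collected from the signing of the ICF until the 8-week follow-up visit". Protocol 1.3 glosses this as "through the 8-week follow-up visit (ie, 8 weeks after the last dose of study drug". Non-serious events are collected only to 4 weeks after the last dose.

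On reporting, SAP 6.7.2 defines serious treatment-emergent events as a subset of TEAEs, and its serious-event tables are all of serious TEAEs. Protocol 9.3.5 limits adverse-event summaries to treatment-emergent events. SAP 6.7.2 also lists all adverse-event data with treatment emergence flagged, and counts deaths without a stated treatment-emergent limit.

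**The concern.** A programmer building the serious-TEAE tables has to choose between SAP 6.7 and 6.7.2, and the choice changes which SAEs are counted. The 6.7.2 rule also rests on a Treatment Period whose end is misdated relative to the last dose, so its reach cannot be read correctly from the SAP.

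Separately, the trial goes on collecting SAEs after either cut-off has closed for subjects who complete dosing, and no table reports them. The affected events could include serious infections or malignancies, which are events of special interest. Drug is still present in that interval: with the 278-hour half-life in Protocol 2.2.3.4 and simple exponential decline, about 19% remains at 28 days (0.5^(672/278) = 0.187) and 3.5% at 56 days (0.5^(1344/278) = 0.035). The Protocol calls the decline mono- or bi-phasic, so these are rough figures.

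**Working it through.** **Inputs.** Last dose: Week 31 (QW), Week 30 (Q2W) (Protocol 1.3). End of Treatment Period for completers: Week 32 (SAP 5.1.3). SAE collection: 8 weeks, that is 56 days, after the last dose (Protocol 1.3). Study day = 7 × week + 1.

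**Step 1: the plan's own figure.** SAP 5.1.3 writes "Week 32 (four weeks after the last dose". The schedule gives 32 − 31 = 1 week (QW) and 32 − 30 = 2 weeks (Q2W), so the figure is not reproduced. Counting from Week 28, the last on-site dosing column in the Schedule of Activities, gives 32 − 28 = 4. That may explain the slip, but Week 28 is not the last dose.

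**Step 2: cut-offs for subjects who complete dosing in Part B.**

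| | QW | Q2W |
|---|---|---|
| Last dose | Day 218 | Day 211 |
| 6.7 cut-off (last dose + 28) | Day 246 | Day 239 |
| 6.7.2 cut-off (Week 32 = Day 225, + 28) | Day 253 | Day 253 |
| 6.7.2 cut-off, days after last dose | 253 − 218 = 35 | 253 − 211 = 42 |
| Disagreement between the two rules | 35 − 28 = 7 days | 42 − 28 = 14 days |
| 8 weeks after last dose | Day 274 | Day 267 |
| Uncovered under 6.7 | 56 − 28 = 28 days | 56 − 28 = 28 days |
| Uncovered under 6.7.2 | 274 − 253 = 21 days | 267 − 253 = 14 days |

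**Step 3: Part A (QW).** Read as a cut-off, Week 32 (Day 225) is 225 − 218 = 7 days after the last dose, against 35 days under 6.7.2. Here non-serious events are affected too, because they are collected to day 28 after the last dose.

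**Step 4: subjects who stop drug early.** After early termination, the 6.7.2 window is at most 14 + 28 = 42 days after the last dose. Protocol 7.1 encourages subjects who stop drug to remain in the study. Suppose one stops before Week 16, stays to Week 32, and has an SAE 40 days after the last dose. Part B of 6.7 excludes it. Read literally, 6.7.2 includes it, because the Treatment Period is still open. For such subjects 6.7.2 can cover the whole SAE window; the defect is the contradiction.

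**Step 5: expected number of events.** The documents give no SAE rate. Assume 2 to 10 SAEs per 100 patient-years and 200 subjects all completing dosing.

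- 28 days: 200 × 28/365.25 = 15.3 patient-years, so 0.3 to 1.5 SAEs.
- 21 days: 11.5 patient-years, so 0.23 to 1.15.
- 14 days: 7.7 patient-years, so 0.15 to 0.77.

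**The case against.** The best defence is that SAP 6.7 applies only unless otherwise specified, so 6.7.2 can be taken to govern. That is a fair reading, but the SAP does not state it. It would also leave the wrong parenthetical and the 21- or 14-day gap in place.

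Collecting SAEs for longer than the treatment-emergent window is not in itself a contradiction, and the SAP follows Protocol 9.3.5 in tabulating only treatment-emergent events. That stands: the missing SAE table is a reporting weakness, while the error proper lies in the conflicting cut-offs and the misdated Week 32.

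Four other readings are tempting and are not supported.

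- *The 6.7.2 rule reaches 8 weeks, since 4 + 4 = 8.* This needs a last dose at Week 28, which contradicts the dosing schedule.
- *SAE counts in the two regimens are not comparable under 6.7.2.* Completers in both regimens close on Day 253, so follow-up from Day 1 is equal. Only time since last dose differs, by 7 days. Rule 6.7 does the reverse: equal time since last dose, closing on Day 246 or Day 239. The placebo-controlled comparison is untouched for subjects who continue, because Period 1 closes at the first Period 2 dose.
- *Half of the SAE collection window is lost.* Days 29-56 are half only of the stretch after the last dose. The window opens at consent; for QW it is up to 28 + 274 = 302 days, of which 28 is about 9%.
- *Late SAEs disappear.* They stay in the all-AE listing, and deaths are both counted and listed. They are absent from the serious-TEAE tables and from the listing of serious TEAEs.

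**Conclusion.** The cut-offs are wrong as written. SAP 6.7 and 6.7.2 disagree by 7 days (QW) or 14 days (Q2W) for Part B completers, and by 28 days (35 − 7) in Part A if Week 32 is read as a cut-off. SAP 5.1.3 misstates the interval from last dose to Week 32. Because non-serious events are not collected beyond 4 weeks, the Part B conflict mainly concerns SAEs with onset in days 29-35 (QW) or 29-42 (Q2W), together with subjects who stop drug early and stay in the study. For completers no rule reaches the 8-week SAE limit.

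The practical size is small: at the assumed rates, up to about 1.5 SAEs fall in the uncovered time. Safety reporting carries no p-values, and no efficacy conclusion changes. The point still merits correction because it decides which serious events are tabulated. The day counts assume dosing and visits at nominal weeks.

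**What to change.** 1. In SAP 5.1.3, delete the parenthetical that dates Week 32 relative to the last dose.
2. In SAP 6.7 and 6.7.2, for Parts A and B, use one treatment-emergent cut-off: 28 days after each subject's actual last dose. This matches the collection period for non-serious events.
3. Add one table of all SAEs with onset through 56 days after the last dose. Use a fixed number of days, not the follow-up visit: for completers that visit is at Week 39, which is 39 − 31 = 8 weeks after the last QW dose but 39 − 30 = 9 weeks after the last Q2W dose, so anchoring on it would give Q2W 7 extra days.

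The cost is SAP wording and one table; no new data are needed. The SAE and non-serious windows will differ and need a footnote. Any Q2W SAE recorded in days 57-63 would appear only in the listing.

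### SAP 6.7 assigns adverse events to Period 1 or 2 by calendar date, in conflict with SAP 5.1.3 and 6.7.2, so an event that arose before dosing on the Week 16 dosing day has no settled period

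*SAP*

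**What the plan says.** Three parts of the SAP draw the line between the placebo-controlled period and the period after the switch.

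- **SAP 6.7 (Safety)** uses the date. A Period 1 event must have its onset on or after the first Period 1 dosing day "and before the date of the first dose received in Period 2". For Period 2, "AEs will be included if date of onset is on or after the day of first dose received in Period 2". Time of day plays no part. Period 2 results are "summarized by the randomized treatment groups (Placebo Izokibep QW; Placebo Izokibep Q2W; Izokibep QW; Izokibep Q2W"), so subjects who began on placebo appear there as placebo-to-izokibep groups. The section opens with a qualifier: "For all Safety Tables, data in Part A and Part B will be summarized as follows, unless otherwise specified".
- **SAP 5.1.3 (Treatment Period)** uses the sequence within the visit. Period 1 is to "end at Week 16 when Week 16 assessments are completed and before administration of study drug", and Period 2 begins with the first administration at or after Week 16.
- **SAP 6.7.2 (Adverse Events)** uses date and time: "TEAEs for period 2 in Part B are either events with start date and time after the start of administration of Week 16 treatment", or earlier events that worsen after that administration.

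The protocol fixes the order of events on the day. Footnote n of the Schedule of Activities (Protocol 1.3) states: "Administration of study drug should be done last after all study procedures unless indicated otherwise". Protocol 4.1.2 has placebo subjects switch once the Week 16 procedures are complete.

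**The concern.** On a Week 16 visit that includes dosing, everything assessed that day comes before the first Period 2 dose. An adverse event dated to such an assessment arose on Period 1 treatment, yet the date rule in 6.7 places it in Period 2. For a placebo subject, it would then be shown in a placebo-to-izokibep group although no izokibep had been given.

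Weeks 0 to 16 are the only placebo-controlled safety comparison in the trial, and Protocol 9.3.5 asks for placebo subjects' events to be shown separately before and after the switch. Two programmers working from this SAP could produce different tables from the same data. One Week 16 abnormality could also be treated in two ways. The blood draw belongs to Period 1 by 5.1.3, which matters for the Hy's Law tables split by period in SAP 6.7.3.1, while an adverse event dated to that draw would be Period 2 by 6.7.

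**Working it through.** The plan gives no figure to reproduce. The check applies each rule to example events and then counts what is scheduled at Week 16.

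**1. Applying the rules.** Assume, for illustration only, that the first Period 2 dose is given on Day 113 (16 × 7 + 1) at 11:00.

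- Rule A (SAP 6.7): Period 1 if onset day < 113, otherwise Period 2.
- Rule B (SAP 5.1.3 and 6.7.2): Period 2 if onset day and time fall after Day 113, 11:00, otherwise Period 1.
- The last column shows the result if an event must satisfy both the 6.7 window and the 6.7.2 definition to enter a table of treatment-emergent events.

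| Event | Rule A | Rule B | Both required |
|---|---|---|---|
| Onset Day 110, reported at the Week 16 visit | 1 | 1 | 1 |
| From an assessment on Day 111, two days before dosing | 1 | 1 | 1 |
| Onset Day 113, 09:00 (before the dose) | 2 | 1 | neither |
| Onset Day 113, no time recorded, taken as 00:00 (assumption) | 2 | 1 | neither |
| Onset Day 113, 12:00 (after the dose) | 2 | 2 | 2 |
| Onset Day 114 | 2 | 2 | 2 |

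The rules disagree only when the onset date equals the dosing date and the onset is before the dose, or is treated as such. A subject with no Period 2 dose has no such boundary: 6.7 keeps that subject's events in Period 1 up to 28 days after the last dose.

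**2. What is scheduled at Week 16.** Post-baseline assessments through Week 16, from the Schedule of Activities:

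| Assessment | Weeks | Share at Week 16 |
|---|---|---|
| ECG | 16 | 1 of 1 |
| Fasting lipids | 16 | 1 of 1 |
| HbA1c | 16 | 1 of 1 |
| Urinalysis | 8, 12, 16 | 1 of 3 (33%) |
| Hematology/chemistry, CRP, C-SSRS | 4, 8, 12, 16 | 1 of 4 (25%) |

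If Rule A governs, an event dated to a scheduled ECG, lipid or HbA1c assessment cannot count in Period 1 for a subject assessed and dosed at Week 16 on the same day.

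**3. Weight of one subject, at planned group sizes.**

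- Placebo-to-izokibep group of 28 to 29: 1/29 = 3.4 and 1/28 = 3.6 percentage points.
- Izokibep arm of 56 to 57: 1/57 = 1.8 and 1/56 = 1.8 percentage points.

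**4. Number affected.** This cannot be derived. The documents give no rate of adverse events with onset on the Week 16 dosing day.

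**The case against.** The strongest reply is that the SAP already gives the right answer. Section 6.7 is a default that yields to other specifications, and 6.7.2, the section specific to adverse events, sets a date-and-time rule. On that reading a timed pre-dose event is a Period 1 event. The reading is reasonable but not secured: the sentences in 6.7 are themselves specific to adverse events, and nothing says which section prevails.

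A reader might infer that everything first found at Week 16 leaves the controlled comparison and is charged to izokibep. The documents do not support that. The rule turns on date of onset, not of detection. A laboratory or ECG finding becomes an adverse event only if judged clinically significant (Protocol 8.2.5 and 10.3.1), and no passage makes the sample date its onset date. Nor is Period 2 placement certain, since joint application of the rules leaves the event in neither period.

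The underlying data also stay visible. Week 16 laboratory and vital sign values are tabulated at the nominal visit (SAP 5.1.4, 6.7.3, 6.7.4), ECG and C-SSRS results are listed, and all adverse events are listed with their relative start day. The rule is the same in every arm, and Protocol 9.3.5 plans no p-values for safety. All of this stands and limits the harm.

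A date cut-off has one merit. Untimed injection site reactions on the dosing day stay with the dose that probably caused them. They were the most common related event in the psoriasis study (38.9%, Protocol 2.2.3.3). A repair should keep that.

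**Conclusion.** The point holds as a contradiction within the SAP. For one class of event, with onset on the day of the first Period 2 dose but before it, the plan supports three allocations: Period 2, Period 1 or neither. The class is narrow but falls at the end of the only placebo-controlled safety comparison, and for ECG, lipids and HbA1c it coincides with the single scheduled post-baseline assessment of that period.

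The size can be stated only per subject, as in the working, using planned group sizes; the weight is larger if fewer subjects are dosed. The conclusion assumes that assessment and dosing happen on the same day in the order the protocol requires, and that some adverse events are dated to that day. The documents do not show whether onset time is collected. The efficacy analyses are unaffected. It would go too far to say that the plan definitely moves Week 16 findings to izokibep, or to attach an expected number of misplaced events.

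**What to change.** Rewrite the adverse event sentences in SAP 6.7 to agree with 5.1.3 and 6.7.2, following the convention 5.1.3 already uses for Day 1, where same-day events go to treatment unless their time shows that they came earlier:

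- An event with onset on the day of the first Period 2 dose belongs to Period 2 by default.
- It belongs to Period 1 if its recorded onset time is before the dose, or if a blinded review completed before unblinding shows that it was a finding of a pre-dose Week 16 assessment.
- Other same-day events without a time, such as injection site reactions, stay in Period 2. State that this overrides any imputed time, because taking a missing time as 00:00 would move them to Period 1.
- Each event is counted in exactly one period, and the same rule applies to the 6.7 windows and the 6.7.2 definitions.

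The cost is a few sentences in the SAP, a change to the period flag, and a short blinded review of same-day events. The review is needed because the documents show no link from an adverse event to the assessment that revealed it. It could be run alongside the review of events of special interest that SAP 6.7.2 already requires before unblinding. The remaining weakness is that untimed events which the review cannot place still rest on a default.
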